10.3.6 Definition of Study Visits

This clinical trial has a total of 9 study visits, including telephone contacts, during the 40-week study (see Table 6.2). The time-on-study for each subject observation will be defined relative to Day 0 of the initial dose of the AP-003-C main study. For the proposed summaries of the data, several “baseline” measures will be utilized.

10.3.7 Number of subjects to receive study drug

Planned enrollment is up to 161 subjects; all subjects that consent to participate in the AP-003-C-OLE study. Assuming a 15% dropout rate, a total of 136 subjects will be enrolled.

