26 MARCH 2018

CLINICAL STUDY PROTOCOL

AN OPEN LABEL EXTENSION STUDY TO ASSESS THE SAFETY OF LONG-TERM TREATMENT WITH A 4-ML INTRA-ARTICULAR INJECTION OF AMPION™ IN ADULTS WITH PAIN DUE TO SEVERE OSTEOARTHRITIS OF THE KNEE

STUDY NUMBER: AP-003-C-OLE

| | |
|---------------------------------|--|
| Drug Development Phase: | Phase 3 |
| Investigational Product: | Ampion™ |
| Indication: | Osteoarthritis of the knee |
| Sponsor: | Ampio Pharmaceuticals, Inc. [name] |
| Date: | Version 3.0 26 March 2018 |

Conduct: In accordance with the ethical principles that originate from the Declaration of Helsinki and that are consistent with International Conference on Harmonization (ICH) guidelines on Good Clinical Practice (GCP) and regulatory requirements as applicable.

Confidential Information

This document is the sole property of Ampio Pharmaceuticals, Inc. This document and any and all information contained herein has to be considered and treated as strictly confidential. This document shall be used only for the purpose of the disclosure herein provided. No disclosure or publication shall be made without the prior written consent of Ampio Pharmaceuticals, Inc.

PROTOCOL SIGNATURE PAGE

I have read and understand the contents of this clinical protocol for Study No. AP-003-C-OLE dated 26 March 2018 and agree to meet all obligations of Ampio Pharmaceuticals, Inc. as detailed in all applicable regulations and guidelines.

Signed By:

<Study personnel signature>

<Enter date>

PROTOCOL SYNOPSIS

| | | |
|---|--|--|
| Sponsor: Ampio Pharmaceuticals, Inc. | Investigational Product: Ampion™ | Developmental Phase: Phase 3 |
| Title of Study: An Open Label Extension (OLE) study to assess the safety of long-term treatment with a 4-mL intra-articular injection of Ampion™ in adults with pain due to severe osteoarthritis of the knee | | |
| Protocol Number: AP-003-C-OLE | | |
| Study Center(s): Approximately 14 sites | | |
| Indication: Severe osteoarthritis of the knee (OAK) (Kellgren Lawrence Grade 4, KL 4) | | |
| Number of subjects: Up to 161 subjects | | |

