3 STUDY DESIGN

3.1 STUDY DESIGN OVERVIEW

Subjects who have completed the AP-003-C main study (n=161) will be offered the option to roll-over to the open label extension study (AP-003-C-OLE) at their final visit of the AP-003-C main study (Visit 7). Enrollment into the AP-003-C-OLE study (Visit 9) allows a 170-day screening window from the AP-003-C main study Visit 7. AP-003-C-OLE study will include the following visits:

Visit 9/Enrollment (Day-170 to Day 0, but not to occur before completion of AP-003-C main study) in-office visit, Visit 10 (24 hours after enrollment post injection follow-up telephone call), Visit 11 in-office visit (Day 84 ±14 days), Visit 12 (24 hours after Visit 11 post injection follow-up telephone call), Visit 13 in-office visit (Day 168 ± 14 days), Visit 14 (24 hours after Visit 13 post injection follow-up telephone call), Visit 15 in-office visit (Day 252 ± 14 days), Visit 16 (24 hours after visit 15 post injection follow-up telephone call), Visit 17 final in-office visit (Day 280 ± 14 days).

The safety of repeat dosing will be evaluated at all visits; in-office visit safety assessments will include vital signs, physical exams, evaluation of AEs, and laboratory analysis. Phone visits will evaluate for AEs.

The clinical effects of treatment on OA pain will be evaluated during all in-clinic visits using the Western Ontario and McMaster Universities Arthritis Index (WOMAC®) osteoarthritis Index 3.1 and the Patient's Global Assessment of disease severity (PGA). The WOMAC will also be utilized to assess the contralateral knee pain at Enrollment/Visit 9 and Visit 17 (or Early Termination Visit).

The WOMAC® is a validated pain scoring system and sets the standard for the subject response. In order not to bias the collection of data, only questions from the validated WOMAC pain scale will be asked of subjects.

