4 SELECTION OF SUBJECTS

4.1 NUMBER OF SUBJECTS

A total of approximately 161 subjects will be enrolled from the AP-003-C main study into the AP-003-C-OLE study.

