4.2 INCLUSION CRITERIA

1. Participation and completion in the AP-003-C study
2. Able to provide written informed consent to participate in the study
3. Willing and able to comply with all study requirements and instructions of the site study staff
4. Male or female, 40 years to 85 years old (inclusive), as assessed in the AP-003-C main study
5. Must be ambulatory, as assessed in the AP-003-C main study
6. Study knee must have a clinical diagnosis of OA and supported by radiological evidence (Kellgren Lawrence Grade 4) as assessed in the AP-003-C main study.
7. Moderate to moderately-severe OA pain in the index knee (rating of at least 1.5 on the WOMAC Index 3.1 5-point Likert Pain Subscale), as assessed in the AP-003-C main study
8. Moderate to moderately-severe OA function in the index knee (rating of at least 1.5 on the WOMAC Index 3.1 5-point Likert Function Subscale), as assessed in the AP-003-C main study
9. WOMAC A, 5-point Likert pain subscale <1.5 in the contralateral knee, as assessed in the AP-003-C main study
10. Ability to discontinue NSAID ± 72 hours before/after injections (in-office visits). Low-dose Aspirin (81 mg) is allowed during the study but must not be taken at least 24 hours prior to in-office visits.
11. No analgesia (including acetaminophen [paracetamol]) taken 24 hours prior to an efficacy measure

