2.4 Sample Size

The original AP-003-C study used total of 170 subjects (140 Ampion; 25 Saline) to test the following hypotheses.

$$H_0: \pi \leq 30\% \text{ versus } H_A: \pi > 30\%$$

This study is observational, using subjects who consent from the AP-003-C study, so no formal sample size was calculated. In following ICH E1A safety guidelines to assess clinical safety in long-term treatment of non-life-threatening conditions, it is anticipated that 100 subjects will be enrolled into this study.

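### Enrolment is stated as about 161, 136 and 100, and the planned tables may not show how many subjects received the five Ampion injections named in the primary objective

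*Protocol*

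**What the plan says.** **Size.** Protocol 3.1: "Subjects who have completed the AP-003-C main study (n=161) will be offered the option to roll-over". The synopsis gives "Number of subjects: Up to 161 subjects". Protocol 4.1: "A total of approximately 161 subjects will be enrolled from the AP-003-C main study". Protocol 10.3.7: "Planned enrollment is up to 161 subjects; all subjects that consent to participate in the AP-003-C-OLE study", followed at once by "Assuming a 15% dropout rate, a total of 136 subjects will be enrolled". SAP 2.4 says that no formal sample size was calculated, cites a long-term safety guideline, and adds that "it is anticipated that 100 subjects will be enrolled into this study". SAP 4.3 estimates about 160 subjects receiving the injection. SAP 2.4 also gives the main study as 170 subjects, 140 on Ampion and 25 on saline.

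**Exposure.** The primary objective (Protocol 3.2.1, SAP 2.1) is the safety of 12-weekly repeat dosing over 52 weeks and/or five Ampion injections in all, one of them from the main study. Protocol 5, Table 6.1 and SAP 4.3 give four extension injections (Visits 9, 11, 13 and 15). Protocol 10.3.10 instead has Ampion given at every in-clinic visit. Entry requires "Participation and completion in the AP-003-C study", with no restriction by main-study arm; Protocol 1.2 describes a 6:1 randomization. Enrolment "allows a 170-day screening window from the AP-003-C main study Visit 7".

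**Tables and time origin.** SAP 4.1 specifies TEAE incidence with exact binomial intervals and says there is no comparator. Protocol 10.4.2 tabulates adverse events for the overall population. SAP 7 lays out every table by treatment arm without defining the term, and SAP 5.2 defines study drug as Ampion or saline. Protocol 9.3 and 10.3.6 count from the main-study injection; SAP 4.2 counts from the first dose of this study.

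**Interim.** Protocol 10.3.9 plans one; SAP 4.5 says there is none.

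**The concern.** The size statements cannot all describe the same quantity, and the 100 in the SAP follows from nothing else in either document. More important is the denominator behind the primary objective. The extension takes completers from both main-study arms, so the safety population mixes subjects whose first Ampion dose was in the main study with subjects whose first was at Visit 9. A pooled TEAE percentage answers how often events occurred among everyone dosed. It does not say how many of those subjects had five Ampion injections, or a year since their first one. In a descriptive safety study those denominators are the main product.

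**Working it through.** **1. The plan's 136.** 161 × (1 − 0.15) = 136.85, and 160 × 0.85 = 136.0, so the figure reproduces. It can mean (a) 161 enrol and about 136 complete, or (b) 161 are offered roll-over, 15% do not take it up, and 136 enrol. Under (b) the documents give no in-study dropout rate. The SAP's 100 fits neither: reaching it from 161 needs a loss of 1 − 100/161 = 37.9%.

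**2. Main-study counts.** 140 + 25 = 165, not 170. At 6:1, 170 would split 145.7 to 24.3.

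**3. Maximum exposure under the four-injection schedule.** Prior Ampion: 1 + 4 = 5 injections. Prior saline: 0 + 4 = 4. At Visit 17 a prior-saline subject is 280/7 = 40 weeks from first Ampion, or 294/7 = 42 at the late edge of the window. Such a subject meets the 52-week part of the objective only if time after saline is counted. Protocol 10.3.10 read literally covers five in-clinic visits (9, 11, 13, 15, 17) and gives a different count; the passages must be reconciled.

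**4. Prior-saline share.** Assumption: roll-over does not depend on arm. The prior-Ampion share p is 140/165 = 0.848 (SAP counts) to 6/7 = 0.857 (randomization ratio). Prior-saline subjects among 161: 161 × 25/165 = 24.4 to 161/7 = 23.0.

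**5. Completers with five Ampion injections** = n × (1 − d) × p. Assumptions: dropout d does not depend on arm, and completers attended every injection visit.

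| Enrolled n | d = 0 (ceiling) | d = 15% | d = 30% |
|---|---|---|---|
| 161 | 136.6–138.0 | 116.1–117.3 | 95.6–96.6 |
| 136 | 115.4–116.6 | 98.1–99.1 | 80.8–81.6 |
| 100 | 84.8–85.7 | 72.1–72.9 | 59.4–60.0 |

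The 136 row applies under reading (b); its 15% column adds a second loss that the documents do not state. A subject who leaves after Visit 15 also has five injections, so the number dosed five times lies between the completer figure and the ceiling.

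**6. Precision.** With no events seen, the upper limit of the two-sided exact 95% interval is 1 − 0.025^(1/n):

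| n | Upper limit |
|---|---|
| 161 (all dosed) | 2.3% |
| 116–117 | 3.1% |
| 72–73 | 4.9–5.0% |
| 23–24 (prior saline) | 14–15% |

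**7. Roll-over gap and interim.** At nominal timing the first extension injection falls 84 to 84 + 170 = 254 days after the main-study injection. The interim counts 52 weeks (364 days) from that injection, which is extension Day 280 with no gap (four extension injections due) but Day 110 with the longest gap (two due, at Days 0 and 84). Having reached 52 weeks therefore does not fix the number of injections.

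**The case against.** The best defence is that the study is descriptive. Enrolment is whoever consents, no hypothesis is tested and no sample size was calculated, so a loose planning figure changes nothing in conduct. That stands, and it limits the point to reporting.

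Several stronger readings are tempting, and the documents do not support them:

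- *That 136 is an arithmetic error.* If the 15% is the share who do not roll over, 136 is correct as enrolment. The defect is that the meaning is not stated, and that Protocol 4.1 expects about 161.
- *That four sizes conflict.* A ceiling of 161 and an estimate of about 160 agree. The outlier is the 100; the ambiguous figure is the 136.
- *That prior-saline subjects can never have five injections.* This holds under the four-injection schedule, but Protocol 10.3.10 contradicts that schedule.
- *That the primary TEAE analysis is undefined.* SAP 4.1 and Protocol 10.4.2 specify the overall pooled summary. Treatment arm may simply be carried over from the main study, like the randomization listing and the 12-week figures in SAP 7.
- *That as many as 28 of 161 are prior-saline.* This uses 140/170, which implies 30 saline subjects where SAP 2.4 states 25.

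SAP 7 also refers to a separate document that is not available here and might contain exposure displays. None of this supplies the missing link between the five-injection objective and a denominator: the listed titles name neither exposure nor prior arm.

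**Conclusion.** The point holds as an inconsistency in stated size together with a reporting gap on the primary objective. It should be corrected, but it invalidates no analysis. The conflicts that remain on any reading are the SAP's 100 against its own 160, the main-study total of 170 against 165, and the interim that one document plans and the other excludes. On exposure, 23–24 of 161 would be prior-saline and limited to four Ampion injections under the four-injection schedule. Completers with five would be 116–117 if 161 enrol and 15% drop out in-study, or 72–73 if only 100 enrol. If 136 is already net of non-roll-over, the ceiling is 115–117, and 98–99 only if a further 15% loss is assumed. All of these rest on roll-over and dropout being unrelated to main-study arm, which the documents do not establish. For an event never observed, moving from all 161 dosed to the five-injection completers raises the upper limit from 2.3% to 3.1%, or to about 5% at an enrolment of 100.

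**What to change.** - State one enrolment figure in both documents, and say whether 136 counts completers or roll-overs.
- Correct or explain the 100 in SAP 2.4, and correct 140/25/170 from the main-study record.
- Reconcile Protocol 10.3.9 with SAP 4.5, and Protocol 10.3.10 with Protocol 5, Table 6.1 and SAP 4.3.
- Correct the study-drug definition in SAP 5.2, define or drop treatment arm in SAP 7, and state one TEAE start, reconciling Protocol 9.3 and 10.3.6 with SAP 4.2 and 5.2. The choice decides whether the main-study injection appears in the TEAE tables.
- Keep the all-dosed safety population as primary. Add an exposure table: cumulative Ampion injections, time since first Ampion, and roll-over gap.
- Add descriptive TEAE summaries by prior main-study arm and by cumulative Ampion injections at onset, with at-risk denominators. Note that subjects who stop for an adverse event fall into the lower-exposure groups.
- Quote an expected five-injection number only with its assumptions, and label precision bounds as two-sided 95% limits.

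The cost is wording and a little more tabulation, with no added subjects or visits. The drawbacks are imprecise rates in the small prior-saline group and a stated exposure that looks less favourable.

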10.3.8 Disposition of subjects

Disposition of subjects, including study completion status, safety profile, and response to therapy as measured by WOMAC and PGA, will be summarized by age group, race and gender for each of the analysis populations.

10.3.9 Interim analysis

An interim analysis will occur when approximately 80 subjects have reached 52 weeks of time following the first injection at Visit 1 of the AP-003-C main study, regardless of what study visit they have completed in the AP-003-C-OLE study.

10.3.10 Blinding and randomization

No blinding or randomization is required for the AP-003-C-OLE study. All subjects will receive Ampion™ 4-mL at each in-clinic visit.

10.3.11 Data presentation

10.3.11.1 Demographic and Baseline Characteristics:

Demographic (e.g., age, sex, race, ethnicity) and baseline characteristics (e.g., weight, height) summarized using descriptive statistics, overall and by treatment group for the ITT analysis population.

10.3.11.2 Medical History and Physical Examination:

The number and percent of subjects with past and current medical disorders at the time of enrollment will be presented overall and by treatment group for the ITT analysis population. Results of any abnormalities documented from the physical examination will be summarized overall and by treatment group for the safety and ITT analysis populations.

10.3.11.3 Concomitant Medications or Treatments:

The number and percent of subjects receiving concomitant medications or treatments prior to and during the study and at the final visit will be tabulated and presented overall and by treatment group for the ITT analysis population. Concomitant medications/treatments will be summarized using descriptive statistics and will be presented by type of drug (WHO DRUG classification) overall and by treatment group for the safety and ITT analysis populations.

10.3.11.4 Safety data:

Safety data will be evaluated by changes in vital sign measurements and the frequency and severity of AEs. Concomitant medication will be recorded for safety.

Adverse events:

The Investigator is responsible for monitoring the safety of subjects who have enrolled in the study. All AEs considered to be possibly related to Ampion™ will be followed until the event resolves or stabilized without further change. Subjects will be followed for the occurrence of AEs until completion of the study at Visit 17 or until early termination from the study (if applicable).

Investigators are required to document all AEs occurring during the clinical trial, commencing with the first day of treatment and including the protocol-defined post-treatment follow-up period on the appropriate CRF pages.

The severity of AEs (mild, moderate, severe), relatedness (related, possibly related, unrelated) along with the duration, action taken, and outcome (e.g., study withdrawal) will also be recorded. In addition, events meeting the criteria of a Serious Adverse Event (SAE) must be reported to the Sponsor within 24 hours on the SAE reporting forms.

10.3.11.5 Efficacy data:

All efficacy variables will be assessed at Visit 9 (Day 0), Visit 11 (Day 84 ± 14), Visit 13 (Day 168 ± 14), Visit 15 (Day 252 ± 14), and Visit 17 (Day 280 ± 14). Except where noted to be otherwise, all statistical tests will be two-sided and will be at the 5% level of significance.

Unless otherwise specified, continuous variables will be summarized with the number of non-missing observations, mean, standard deviation, median, minimum, and maximum displayed. Categorical data will be summarized as counts and percentages. All efficacy assessments will be summarized as the measured value and as the change from baseline by treatment at each time point. Summary statistics will include number of observations, mean, standard deviation, median, minimum and maximum. Change from baseline will also include a 95% confidence interval.

Except where otherwise specified, missing data will not be estimated or carried forward in any of the descriptive analyses. No multiple comparison adjustment will be made for the secondary efficacy analyses. Data transformation or use of rank-based tests may be used if endpoints depart substantially from a normal distribution.

Baseline (Day 0 of AP-003-C main study) is defined as the last pre-treatment assessment. Because the secondary analyses are considered supportive to the primary analysis (i.e., not required to demonstrate efficacy of the test article), there is no requirement under ICH to adjust for multiplicity

10.4 STUDY ENDPOINTS

10.4.1 Primary Endpoint

- Incidence and severity of treatment-emergent adverse events (TEAEs).

These incidents will be summarized by number and percent of subjects having an event, the number of events per subject, and frequency of events in study population.

10.4.2 Exploratory Endpoints

- Responder status based on the OMERACT-OARSI responder criteria from Enrollment/Visit 9 (Day 0) to Visits 11, 13, 15, and 17
- Evaluate 20% improvement in Pain and Function and 0.5 point absolute change in the 5-point Likert Scale from Enrollment/Visit 9 (Day 0) to Visits 11, 13, 15, and 17
- Evaluate 20% improvement in PGA and 0.5 point absolute change in the 5-point Likert Scale
- Mean change in WOMAC A pain subscore between Visit 1/Day 0 (AP-003-C main study) and Enrollment/Visit 9 (Day 0) to Visits 11, 13, 15, and 17 (AP-003-C-OLE)
- Percent change in WOMAC A pain subscore between Visit 1/Day 0 (AP-003-C main study) and Enrollment/Visit 9 (Day 0) to Visits 11, 13, 15, and 17 (AP-003-C-OLE)
- Mean change in WOMAC B stiffness subscore between Visit 1/Day 0 (AP-003-C main study) and Enrollment/Visit 9 (Day 0) to Visits 11, 13, 15, and 17 (AP-003-C-OLE)
- Percent change in WOMAC B stiffness subscore between Visit 1/Day 0 (AP-003-C main study) and Enrollment/Visit 9 (Day 0) to Visits 11, 13, 15, and 17 (AP-003-C-OLE)
- Mean change in WOMAC C physical function subscore between Visit 1/Day 0 (AP-003-C main study) and Enrollment/Visit 9 (Day 0) to Visits 11, 13, 15, and 17 (AP-003-C-OLE)
- Percent change in WOMAC C physical function subscore between Visit 1/Day 0 (AP-003-C main study) and Enrollment/Visit 9 (Day 0) to Visits 11, 13, 15, and 17 (AP-003-C-OLE)
- Mean change in PGA between Visit 1/Day 0 (AP-003-C main study) and Enrollment/Visit 9 (Day 0) to Visits 11, 13, 15, and 17 (AP-003-C-OLE)
- Percent change in PGA between Enrollment/Visit 9 (Day 0) to Visits 11, 13, 15, and 17 (AP-003-C-OLE)
- Mean Change in WOMAC A pain subscore questions 1 and 2 (pain with movement) between Visit 1/Day 0 (AP-003-C main study) and Enrollment/Visit 9 (Day 0) to Visits 11, 13, 15, and 17 (AP-003-C-OLE)

- Percent Change in WOMAC A pain subscore questions 1 and 2 (pain with movement) between Visit 1/Day 0 (AP-003-C main study) and Enrollment/Visit 9 (Day 0) to Visits 11, 13, 15, and 17 (AP-003-C-OLE)
- Mean Change in WOMAC A pain subscore questions 3–5 (resting pain) between Visit 1/Day 0 (AP-003-C main study) and Enrollment/Visit 9 (Day 0) to Visits 11, 13, 15, and 17 (AP-003-C-OLE)
- Percent Change in WOMAC A pain subscore questions 3–5 (resting pain) between Visit 1/Day 0 (AP-003-C main study) and Enrollment/Visit 9 (Day 0) to Visits 11, 13, 15, and 17 (AP-003-C-OLE)
- Change in contralateral knee pain (WOMAC A) between Visit 9 and Visit 17
- Change in contralateral knee stiffness (WOMAC B) between Visit 9 and Visit 17
- Change in contralateral knee function (WOMAC C) between Visit 9 and Visit 17
- Time to Total Knee Replacement (TKR)
- Use of rescue analgesia (amount of acetaminophen used)

Exploratory efficacy analyses include the mean change and percent change in WOMAC A, WOMAC B, WOMAC C, WOMAC A1-2, WOMAC A3-5, PGA and amount of acetaminophen used from Visit 1 to Visit 17 using an analysis of covariance model, adjusted for baseline value.

Percent responders using the OMERACT-OARSI responder criteria will be analyzed defined as the percent of subjects whom respond to treatment from Visit 1 to Visit 17. Interim visits will also be analyzed.

1. High improvement in pain or in function $\geq 50\%$ and absolute change in Likert pain scale of ≥ 1 OR
2. Improvement in at least two of the 3 following:
 - a. pain $\geq 20\%$ and absolute change in Likert score ≥ 0.5
 - b. function $\geq 20\%$ and absolute change in Likert score ≥ 0.5
 - c. subject's global assessment $\geq 20\%$ and absolute change in Likert score ≥ 0.5

All of the above endpoints will be evaluated via descriptive statistics and confidence intervals.

The WOMAC Pain Score, the WOMAC Function Score, then PGA score and the OMERACT-OARSI responder criteria, will be analyzed via a repeated measures analysis of variance to determine if there is a significant time effect for these endpoints. Also, to aid in the interpretation of these results, a stability analysis will be performed on these same endpoints. That is, mean pairwise differences between administration time points will be calculated along with their 95% confidence intervals. If stability is achieved at some time point, then the following mean differences should be not be different from zero, in that the confidence interval should include zero.

Adverse events will be tabulated for both number of subjects and number of events by subject and overall study population, summarized by any event, body system, and preferred term. Summaries by serious, severity, and relationship will also be done.

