When the clinical trials of Ampion were designed, it was assumed that the vehicle for the product, saline, would have little to no effect in reducing pain, stiffness, or improving physical function. This control was determined not to be a true placebo, but rather turned out to be active treatment. To address this, Ampio proposed a 12-week Main Study (AP-003-C) with a 6:1 randomization to protect the blind and prevent any potential bias associated with an open label assessment. In follow up to the Main Study, Ampio is adding a 40-week add-on, open label study to address the safety of repeat injections for a year. The Open Label Study will also analyze efficacy using the Western Ontario and McMaster Universities Arthritis Index (WOMAC®) osteoarthritis Index 3.1, and the Patient's Global Assessment of disease severity (PGA). This study will analyze response according to these individual criteria as well as responder analysis of OMERACT-OARSI criteria.

The Osteoarthritis Research Society International (OARSI) and Standing Committee for Clinical Trials Response Criteria Initiative Outcome Measures in Rheumatology (OMERACT) committee, in concert with the international rheumatology community, worked to develop a uniform core set of outcome measures for osteoarthritis. While the committee initially developed two sets of responder criteria to present the results of changes after treatment in three symptomatic domains (pain, function, and patient's global assessment) as a single variable for clinical trials, the committee ultimately worked to create a simplified set of responder criteria, Scenario D, which captured the criteria for response.

In the original plan, for each domain, a response was defined by both a relative and an absolute change, with different cut-offs with regard to the drug, the route of administration and the OA localization. The formal OMERACT-OARSI scenarios defined a responder as:

- a. having achieved a high degree of improvement in pain or a moderate degree of improvement in 2 of the 3 response domains (pain, function, global assessment) (scenario A)

OR

- b. as having achieved a high degree of improvement in either pain or function, or a moderate degree of improvement in 2 of the 3 response domains (scenario B)

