The composite index permits presentation of results of symptom modifying clinical trials in OA based on individual patient responses (responder yes/no). The use of composite indices was still somewhat controversial in that the original OARSI criteria did not account for multiplicity of comparisons, however OMERACT-OARSI worked to rectify this and their conclusions were presented at the OMERACT 6 conference.

OMERACT and OARSI established a task force aimed at evaluating: (1) the variability of observed placebo and active treatment effects using the OARSI responder criteria; and (2) the possibility of proposing a simplified set of criteria. Because individual study endpoints in studies of NSAIDs in patients with hip or knee osteoarthritis were highly correlated, OMERACT-OARSI evaluated six different scenarios to determine whether a simplified set of criteria could be developed. The conclusions of the task force were presented and discussed during the OMERACT 6 conference, where a simplified set of responder criteria (OMERACT-OARSI set of criteria) was proposed. Scenario D was chosen by the members, indicating the importance of having both a relative change and an absolute change as part of the criteria for response.

The criteria for a responder using the Likert Scale, where the 20-point change on the VAS scale is the same as a 1-point change on the Likert Scale and, similarly, the 10-point change in the VAS scale is the same as a 0.5-point change on the Likert Scale, are defined as:

1. High improvement in pain or in function $\geq 50\%$ and absolute change in Likert pain scale of ≥ 1 OR
2. Improvement in at least two of the 3 following:
 - a. pain $\geq 20\%$ and absolute change in Likert score ≥ 0.5
 - b. function $\geq 20\%$ and absolute change in Likert score ≥ 0.5
 - c. patient's global assessment $\geq 20\%$ and absolute change in Likert score ≥ 0.5

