14.2 Efficacy	
14.2.1.1	Summary of OMERACT-OARSI Percent Responder Status (Analysis Population: ITT)
14.2.1.2	Summary of OMERACT-OARSI “controlled” responders (WOMAC A and C)
14.2.1.3	Summary of responders demonstrating a 20% improvement and 0.5 shift in PGA
14.2.1.5	Summary of Patients responding to 50% improvement in Pain and 1.0 absolute change
14.2.1.6	Summary of Patients responding to a 50% improvement in Function and 1.0 absolute change
14.2.1.7	Summary of Patients responding to a 20% improvement in Pain and 0.5 absolute change
14.2.1.8	Summary of Patients responding to a 20% improvement in Function and 0.5 absolute change
14.2.1.9	Summary of Patients responding to a 20% improvement in PGA and 0.5 absolute change
14.2.1.10	Summary of WOMAC A mean change
14.2.1.11	Summary of WOMAC A percent change
14.2.1.12	Summary of WOMAC B mean change
14.2.1.13	Summary of WOMAC B percent change
14.2.1.14	Summary of WOMAC C mean change
14.2.1.15	Summary of WOMAC C percent change
14.2.1.16	Summary of WOMAC A and C mean change
14.2.1.17	Summary of WOMAC A and C percent change
14.2.1.18	Summary of PGA mean change
14.2.1.19	Summary of PGA percent change
14.2.1.20	Summary of WOMAC mean change
14.2.1.21	Summary of WOMAC percent change

Number	Title

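### Criterion 1 of the OMERACT-OARSI responder rule takes the 1-point change from the pain scale only, even when function supplies the 50% improvement; this conflicts with criterion 2 and SAP Table 14.2.1.6, with a small effect on the composite

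*Protocol*

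**What the plan says.** Protocol 10.4.2 defines a responder by either of two criteria.

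- Criterion 1 begins "High improvement in pain or in function" (the words are the same in Protocol 1.2), sets that improvement at 50% or more, and adds an "absolute change in Likert pain scale of" 1 or more. No function-scale change is named.
- Criterion 2 asks for "Improvement in at least two of the 3 following": pain, function and global assessment. Each has its own 20% threshold and its own 0.5-point change.

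SAP 3.2 and 4.1 name the OMERACT-OARSI responder status without spelling it out, and SAP 5.2 does not define it. SAP Section 7 lists the composite as Table 14.2.1.1. It also lists separate high-improvement tables: Table 14.2.1.5, "Summary of Patients responding to 50% improvement in Pain and 1.0 absolute change", and Table 14.2.1.6, "Summary of Patients responding to a 50% improvement in Function and 1.0 absolute change".

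The reference visit is given in two ways. One bullet in Protocol 10.4.2 reads "Responder status based on the OMERACT-OARSI responder criteria from Enrollment/Visit 9 (Day 0) to Visits 11, 13, 15, and 17". Later text in the same section measures response from Visit 1 to Visit 17, and SAP 4.1 calls for the main-study baseline. Entry to the main study required a function "rating of at least 1.5 on the WOMAC Index 3.1 5-point Likert Function Subscale", with the same minimum for pain. No minimum is re-applied at Visit 9.

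**The concern.** Read literally, a subject whose function improves by 50% or more meets criterion 1 only if pain also falls by a full point. That departs from the pattern of criterion 2 a few lines below. It also departs from the natural reading of Table 14.2.1.6, which sits in a run of tables that each pair one domain with one percentage and one absolute change.

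Because the SAP does not restate the composite, the protocol sentence is the only rule available to the programmers. SAP 4.11 requires independent programming of tables, and two careful programmers could code different rules. At stake is whether Tables 14.2.1.1 and 14.2.1.6 classify the same subject consistently, and a small shift in the reported responder percentage.

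**Working it through.** The plan states no figure that depends on this wording, so there is none to reproduce. The check compares two versions of criterion 1, with criterion 2 unchanged.

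- **Literal:** (pain ≥50% or function ≥50%) and pain fall ≥1.
- **Own-domain:** (pain ≥50% and pain fall ≥1) or (function ≥50% and function fall ≥1).

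WOMAC subscales and PGA run from 0 to 4 (Protocol 6.1.1, 6.1.2).

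**1. Who is lost under the literal rule.** A subject with function ≥50% and ≥1 point always meets 2b, so either 2a or 2c makes that subject a responder anyway. One PGA step is 1 point and at least 1/4 = 25%, which meets 2c. (On the one-to-five range implied by SAP 4.10 it is at least 1/5 = 20%, which still meets 2c.) The subjects lost are those with strong function improvement, pain short of 20% or 0.5 points, and no PGA improvement.

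**2. Who is gained under the literal rule.** A pain fall of 1 point is at least 1/4 = 25%, so 2a is met. To be a responder only under the literal rule, the subject must fail 2b: function improves by ≥50% but by less than 0.5 points. Since 0.5 × baseline ≤ fall < 0.5, baseline function must be below 1.0. This cannot happen from a baseline of at least 1.5. It can happen from Visit 9.

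Enumerating all score combinations (5 pain items; 17 function items assumed) agrees. Every lost case meets 2b and neither 2a nor 2c. There are no gained cases with baselines of at least 1.5. With unrestricted baselines, the highest baseline function among gained cases is 0.94.

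**3. Examples, PGA unchanged.**

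| Pain | Function | Criterion 2 | Literal | Own-domain |
|---|---|---|---|---|
| 2.0 to 1.8 (10%, 0.2) | 2.4 to 1.0 (58%, 1.4) | 2b only | No | Yes |
| 2.0 to 1.4 (30%, 0.6) | 2.4 to 1.0 (58%, 1.4) | 2a and 2b | Yes | Yes |
| 2.4 to 1.4 (42%, 1.0) | 0.94 to 0.47 (50%, 0.47) | 2a only | Yes | No |

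The first subject would count in Table 14.2.1.6, on its natural reading, but not in Table 14.2.1.1.

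**4. Size, from the main-study baseline.** Simulation of 400,000 subjects per scenario.

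- From Protocol Table 1.5.2 (Ampion, combined): mean pain change -0.82, SD 0.817. A mean of -0.5 is an assumed alternative.
- Assumed: function changes with the same mean and SD as pain; pain-function change correlation 0.5 to 0.9; correlation of each with PGA change 0.4 or 0.6; baseline pain and function mean 2.1, SD 0.45, correlation 0.7, floored at the entry minimum; baseline PGA mean 2.2, SD 0.7; PGA change 0.8 times the mean pain change, SD 0.9.

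| Mean change | Pain-function corr. | PGA corr. | Literal % | Own-domain % | Difference (points) |
|---|---|---|---|---|---|
| -0.82 | 0.5 | 0.4 | 67.96 | 70.64 | 2.68 |
| -0.82 | 0.7 | 0.4 | 66.77 | 68.19 | 1.42 |
| -0.82 | 0.9 | 0.6 | 64.90 | 65.13 | 0.23 |
| -0.5 | 0.5 | 0.4 | 51.04 | 53.82 | 2.78 |
| -0.5 | 0.9 | 0.4 | 49.46 | 49.71 | 0.25 |

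Across all scenarios the difference is 0.23 to 2.78 points. On 161 subjects that is 0.0023 × 161 = 0.4 to 0.0278 × 161 = 4.5. On the 100 subjects anticipated in SAP 2.4 it is 0.2 to 2.8. Of subjects with strong function improvement, 0.6% to 11.7% end as composite non-responders. The Visit 9 baseline was not simulated.

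**The case against.** The strongest reply is that the pain-scale wording appears in the same form in two protocol sections, so it may be deliberate. The documents nowhere write out the own-domain rule in full, and the title of Table 14.2.1.6 does not say on which scale the 1.0 is measured. This stands. The documents show an inconsistency; they do not by themselves settle which version was meant.

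A reader might also cite the statement in Protocol 1.2 that "for each domain, a response was defined by both a relative and an absolute change" as proof of the own-domain rule. It does not carry that weight. The sentence describes the earlier plan behind scenarios A and B. For Scenario D, the set adopted, the protocol says only that both a relative and an absolute change matter.

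Two stronger consequences are tempting and unsupported. One is that function responders in general are misclassified; step 1 shows that only those with little pain change and no PGA gain are lost. The other is that the component tables ought to sum to the composite. They would not under any wording, because the components overlap and the composite includes a two-of-three route.

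Finally, the endpoint is exploratory. SAP 4.1 plans no hypothesis test and no comparison with a threshold or historical control, and the primary endpoint is TEAEs. This stands and keeps the point minor.

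**Conclusion.** The inconsistency is real, and following the protocol literally would change some classifications. Measured from the main-study baseline, the literal rule can only understate the composite relative to the own-domain rule, by roughly 0.2 to 2.8 percentage points, or about 0 to 5 of 161 subjects. That assumes the entry minimum of 1.5 and the baseline come from the same assessment. The range rests on assumed function and PGA distributions, since the documents give a change distribution for only one measure; it indicates order of magnitude. Measured from Visit 9, as one protocol bullet specifies, errors can run in both directions and the net effect is not quantified. If the main-study baseline of SAP 4.1 governs, the second direction does not arise. No safety conclusion is affected. The point is a low-priority clarification, worth settling before the tables are programmed.

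**What to change.** Reword criterion 1 in Protocol 10.4.2 and 1.2 so that each domain carries its own change: pain improved by at least 50% with a fall of at least 1 on the pain scale, or function improved by at least 50% with a fall of at least 1 on the function scale. Copy the complete two-part rule into SAP 3.2 so that Table 14.2.1.1 matches Tables 14.2.1.5 and 14.2.1.6. If a 1-point pain change is meant to be required of function responders, say so explicitly in both documents and align the definition behind Table 14.2.1.6.

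The text is one line, but Protocol 11.3 requires a written amendment approved by the sponsor, the IRB/IEC and the health authorities, so it is best bundled with other changes. Before choosing, check which wording was used in the main study and for Protocol Table 1.5.3. The documents do not show it, and a different rule here would weaken comparison with those results.
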